14.2.1.4	Average Pain Intensity Related to Fibromyalgia, Weekly Mean NRS Score at Week 12 Versus Baseline NRS Score – Exploratory Analyses – Scatter Plot – Modified Intent-to-Treat Population	MR	
14.2.1.5	Average Pain Intensity Related to Fibromyalgia, Percent Change from Baseline of Weekly Mean NRS Score at Week 12 Versus DSIS Score at Baseline, Exploratory Analyses –Scatter Plot– Modified Intent-to-Treat Population	MR	14.2.1.3
14.2.1.6.1	Average Pain Intensity Related to Fibromyalgia, Percent Change from Baseline of Weekly Mean NRS Score at Week 12 Versus PROMIS _{FM} Fatigue Profile Experience Subscore at Baseline, Exploratory Analyses – Scatter Plot– Modified Intent-to-Treat Population	MR	14.2.1.3
14.2.1.6.2	Average Pain Intensity Related to Fibromyalgia, Percent Change from Baseline of Weekly Mean NRS Score at Week 12 Versus PROMIS _{FM} Fatigue Profile Social Subscore at Baseline, Exploratory Analyses – Scatter Plot– Modified Intent-to-Treat Population	MR	14.2.1.3
14.2.1.6.3	Average Pain Intensity Related to Fibromyalgia, Percent Change from Baseline of Weekly Mean NRS Score at Week 12 Versus PROMIS _{FM} Fatigue Profile Cognitive Subscore at Baseline, Exploratory Analyses – Scatter Plot– Modified Intent-to-Treat Population	MR	14.2.1.3
14.2.1.6.4	Average Pain Intensity Related to Fibromyalgia, Percent Change from Baseline of Weekly Mean NRS Score at	MR	14.2.1.3

Figure Number	Figure Title	Validation Method	Shell Number (if repeat)
	Week 12 Versus PROMIS _{FM} Fatigue Profile Motivation Subscore at Baseline, Exploratory Analyses – Scatter Plot– Modified Intent-to-Treat Population		
14.2.1.7	Average Pain Intensity Related to Fibromyalgia, Percent Change from Baseline of Weekly Mean NRS Score at Week 12 Versus PROMIS Sleep Disturbance Score at Baseline, Exploratory Analyses – Scatter Plot– Modified Intent-to-Treat Population	MR	14.2.1.3
14.2.1.8	Average Pain Intensity Related to Fibromyalgia, Percent Change from Baseline of Weekly Mean NRS Score at Week 12 Versus PROMIS Physical Function Score at Baseline, Exploratory Analyses – Scatter Plot– Modified Intent-to-Treat Population	MR	14.2.1.3
14.2.1.9	Average Pain Intensity Related to Fibromyalgia, Percent Change from Baseline of Weekly Mean NRS Score at Week 12 Versus HADS Depression Score at Baseline, Exploratory Analyses – Scatter Plot– Modified Intent-to-Treat Population	MR	14.2.1.3
14.2.1.10	Average Pain Intensity Related to Fibromyalgia, Percent Change from Baseline of Weekly Mean NRS Score at Week 12 Versus HADS Anxiety Score at Baseline, Exploratory Analyses – Scatter Plot– Modified Intent-to-Treat Population	MR	14.2.1.3
14.2.1.11	Average Pain Intensity Related to Fibromyalgia, Cumulative Response (Percent Reduction from Baseline) in the Weekly Mean NRS Score at Week 12, Secondary Analyses - Modified Intent-to-Treat Population	MR	
14.2.1.12	Average Pain Intensity Related to Fibromyalgia, Time to First $\geq 30\%$ Reduction in Weekly Mean NRS Score – Secondary Analyses - Modified Intent-to-Treat Population	MR	
14.2.1.13	Average Pain Intensity Related to Fibromyalgia, Time to First $\geq 50\%$ Reduction in Weekly Mean NRS Score – Secondary Analyses - Modified Intent-to-Treat Population	MR	14.2.1.11
14.2.1.14	Average Pain Intensity Related to Fibromyalgia, LS Mean Difference in Weekly Mean NRS Score at Week 12, 2-Sided Analyses – Forest Plot – Modified Intent-to-Treat Population	MR	14.2.1.2

[figure not shown]
[REDACTED]

[REDACTED]

[REDACTED]

Listing Number	Listing Title	Validation Method	Shell Number (If Repeat)
16.2	Subject Data Listings		
16.2.1	Discontinued Subjects		
16.2.1.1	Subject Disposition, Early Withdrawal - Randomized Population	IP	
16.2.1.2	Subject Disposition, Screen Failures - Screened Population	IP	
16.2.1.3	Subject Disposition, Ineligible for Randomization - Screened Population	IP	
16.2.2	Protocol Deviations	IP	
16.2.2.1	Protocol Deviations - Screened Population	IP	
16.2.3	Subjects Excluded from The Efficacy Analyses	IP	
16.2.3.1	Analysis Populations - Randomized Population	IP	
16.2.4	Demographic Data	IP	
16.2.4.1	Demographics and Baseline Characteristics - Safety Population	IP	
16.2.4.2	Medical History - Safety Population	IP	
16.2.4.3	Inclusion and Exclusion Criteria - Safety Population	IP	
16.2.4.4	Discontinuation of Analgesic Medications - Safety Population	IP	
16.2.5	Compliance and / or Drug Concentration Data	IP	
16.2.5.1	Study Drug Administration - Safety Population	IP	
16.2.5.2	Study Drug Dispensed and Returned - Safety Population	IP	
16.2.5.3	Study Drug Compliance - Safety Population	IP	
16.2.5.4	Rescue Medication (Acetaminophen 500 mg) Dispensed and Returned	IP	16.2.5.2
16.2.5.5	Concomitant Medications - Safety Population	IP	
16.2.6	Individual Efficacy Response Data	IP	
16.2.6.1	Average Pain Intensity Related to Fibromyalgia in The Past 24 Hours - Weekly Mean NRS Score - Modified Intent-to-Treat Population	IP	
16.2.6.2	Daily Rescue Medication Usage - Modified Intent-to-Treat Population	IP	
16.2.6.3	Daily Sleep Interference Scale - Modified Intent-to-Treat Population	IP	
16.2.6.4	Fibromyalgia Impact Questionnaire – Revised Score - Modified Intent-to-Treat Population	IP	

16.2.6.5	Patient Reported Outcomes Measurement Information System Sleep Disturbance Score - Modified Intent-to-Treat Population	IP	
16.2.6.6	Patient Reported Outcomes Measurement Information System – Fibromyalgia Fatigue Profile Score - Modified Intent-to-Treat Population	IP	
16.2.6.7	Patient Reported Outcomes Measurement Information System Physical Function Score - Modified Intent-to-Treat Population	IP	
16.2.6.8	Patient Global Impression of Severity - Modified Intent-to-Treat Population	IP	
16.2.6.9	Patient Global Impression of Change - Modified Intent-to-Treat Population	IP	
16.2.6.10	Hospital Anxiety and Depression Scale – Modified Intent-to-Treat Population		
16.2.6.11	Sheehan-Suicidality Tracking Scale - Modified Intent-to-Treat Population	IP	
16.2.6.12	Time to First $\geq 30\%$ or $\geq 50\%$ Reduction in Mean NRS Score for Average Pain Intensity Related to Fibromyalgia – Modified Intent-to-Treat Population	IP	
16.2.7	Adverse Event Listings	IP	
16.2.7.1	Adverse Event Data - Safety Population	IP	
16.2.8	Individual Laboratory Measurements and Other Safety	IP	
16.2.8.1	Hematology Data - Safety Population	IP	
16.2.8.2	Serum Chemistry Data - Safety Population	IP	
16.2.8.3	Urinalysis Data - Safety Population	IP	
16.2.8.4	Thyroid Panel Data - Safety Population	IP	
16.2.8.5	Serology Data - Safety Population	IP	
16.2.8.6	Vital Signs Data - Safety Population	IP	
16.2.8.7	Electrocardiogram Data - Safety Population	IP	
16.2.8.8	Physical Examination Data - Safety Population	IP	
16.2.8.9	Neurological Examination Data - Safety Population	IP	
16.2.8.10	Urine Pregnancy Testing Data - Safety Population	IP	
16.2.8.11	Urine Drug Screening Data - Safety Population	IP	

Study Name: A Randomized, Double-Blind, Placebo-Controlled Study to Assess the Efficacy and Safety of NYX-2925 in Subjects with Fibromyalgia

Statistical Analysis Plan (SAP)
Version being approved: NYX-2925-2005_SAP_V1.0, dated 21July2022

Tables, Figures and Listings
(TFL) Shell version being
approved: NYX-2925-2005_TFL_Shells_V1.0, dated 21July2022

1. BACKGROUND

This document details changes and / or additions to the planned statistical analyses for Aptinyx Inc, protocol NYX-2925-2005 study titled “A Randomized, Double-Blind, Placebo-Controlled Study to Assess the Efficacy and Safety of NYX-2925 in Subjects with Fibromyalgia” previously described in V1.0 of the Statistical Analysis Plan (SAP) dated 21-JUL-2022.

These amendments were made post database lock and after the study was unblinded.

Rationale for Addendum:

- 1) To detail the Baseline Observation Carried Forward (BLOCF) imputation used in primary efficacy analysis
- 2) To update the definition of prior medication
- 3) To update the title of outputs:

Output Number and Title	Requested Change
Table 14.2.2.2.1 Patient Global Impression of Change, Change from Baseline to until Week 12, Mixed Model for Repeated Measures – 1-Sided Test – Modified Intent-to-Treat Population	Change the title to ‘Patient Global Impression of Change by Visit, Mixed Model for Repeated Measures – 1-Sided Test – Modified Intent-to-Treat Population’
Table 14.2.2.2.2 Patient Global Impression of Change, Change from Baseline to until Week 12, Mixed Model for Repeated Measures – 2-Sided Test – Modified Intent-to-Treat Population	Change the title to ‘Patient Global Impression of Change by Visit, Mixed Model for Repeated Measures – 2-Sided Test – Modified Intent-to-Treat Population’

In addition to the above changes and / or additions, a number of minor changes have been made to the shells so that they reflect the presentation of the final set of tables, figures and listings (TFLs). These changes have not been detailed here.

2. CHANGES TO EXISTING SAP

2.1 Change 1

2.1.1 Original text

Section 6.8 Prior and Concomitant Medications

Separate tabulations will be produced for prior and concomitant medications presented by treatment group and overall, for the Safety Population. For reporting purposes, prior medications are defined as all medications taken within 30 days of the Screening visit but stopping before the date of first dose of study drug.

Concomitant medications are defined as medications taken on or after the date of first dose of study drug, including medications initiated prior to the first dose of study drug and continuing after first dose of study drug. Medications for which a stop date is not recorded will be designated ongoing at end of study. Prior and concomitant medications will be summarized using Anatomic Therapeutic Chemical (ATC) Level 3 and Preferred Name.

2.1.2 New text

Section 6.8 Prior and Concomitant Medications

Separate tabulations will be produced for prior and concomitant medications presented by treatment group and overall, for the Safety Population. For reporting purposes, prior medications are defined as all medications taken and stopping before the date of first dose of study drug. Concomitant medications are defined as medications taken on or after the date of first dose of study drug, including medications initiated prior to the first dose of study drug and continuing after first dose of study drug. Medications for which a stop date is not recorded will be designated ongoing at end of study. Prior and concomitant medications will be summarized using Anatomic Therapeutic Chemical (ATC) Level 3 and Preferred Name.

2.2 Change 2

2.2.1 Original Text

Section 6.11.1.1 Estimand

The primary efficacy analysis will evaluate the treatment-policy estimand to estimate the improvement (reduction) from Baseline in the weekly mean of the daily NRS score in subjects in the modified ITT population not discontinuing treatment early due to an AE or lack of efficacy through Week 12.

The following four attributes describe the estimand that will be used to define the treatment effect of interest for the primary efficacy analysis:

- Population = Subjects meeting the protocol-specified inclusion/exclusion criteria, who received at least one dose of study drug and who have at least one post-baseline assessment of the pain intensity NRS.
- Subject-level outcome = Change from baseline in the weekly mean of the daily NRS score assessing average pain intensity in the past 24 hours

- Intercurrent event handling = An intercurrent event is defined as discontinuation of study drug due to an AE or lack of efficacy prior to Week 12. For the analysis, baseline Observation Carried Forward (BLOCF) imputation will be used to impute data for visits after a patient has discontinued randomized treatment due to either of these reasons (even if data is present).
- Population-level summary measure = Difference in least squares (LS) mean change from baseline in the weekly mean of the daily NRS score at Week 12, comparing each dose of NYX-2925 to placebo.

Any missing data at Week 12 that are not preceded by an intercurrent event (i.e., discontinuation of study drug due to AE or lack of efficacy) will remain as missing.

2.2.2 New Text

The primary efficacy analysis will evaluate the treatment-policy estimand to estimate the improvement (reduction) from Baseline in the weekly mean of the daily NRS score in subjects in the modified ITT population not discontinuing treatment early due to an AE or lack of efficacy through Week 12.

The following four attributes describe the estimand that will be used to define the treatment effect of interest for the primary efficacy analysis:

- Population = Subjects meeting the protocol-specified inclusion/exclusion criteria, who received at least one dose of study drug and who have at least one post-baseline assessment of the pain intensity NRS.
- Subject-level outcome = Change from baseline in the weekly mean of the daily NRS score assessing average pain intensity in the past 24 hours
- Intercurrent event handling = An intercurrent event is defined as discontinuation of study drug due to an AE or lack of efficacy prior to Week 12. For primary efficacy analysis purposes, baseline Observation Carried Forward (BLOCF) imputation will be used to impute data for visits after a patient has discontinued randomized treatment due to either of these reasons (even if data is present).
- Population-level summary measure = Difference in least squares (LS) mean change from baseline in the weekly mean of the daily NRS score at Week 12, comparing each dose of NYX-2925 to placebo.

Any missing data at Week 12 that are not preceded by an intercurrent event (i.e., discontinuation of study drug due to AE or lack of efficacy) will remain as missing.

2.3 Change 3

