12.6. Analyses of Efficacy

12.6.1. Primary Efficacy Analysis

The primary efficacy analysis will be performed based on the modified Intent-to-Treat population.

The primary efficacy endpoint is the change from baseline in the weekly mean of the daily NRS score assessing average pain intensity in the past 24 hours. The primary efficacy analysis will evaluate the treatment-policy estimand in the modified Intent-to-Treat population. The treatment-policy estimand combines the improvement (reduction) from Baseline in the weekly mean of the daily NRS score and not discontinuing treatment early due to an AE or lack of efficacy through Week 12.

The following four attributes describe the estimand that will be used to define the treatment effect of interest for the primary efficacy analysis:

1. Population = Subjects meeting the protocol-specified inclusion/exclusion criteria, who received at least one dose of study drug and who have at least one post-baseline assessment of the pain intensity NRS.
2. Subject-level outcome = Change from baseline in the weekly mean of the daily NRS score assessing average pain intensity in the past 24 hours
3. Intercurrent event handling = An intercurrent event is defined as discontinuation of study drug due to an AE or lack of efficacy prior to Week 12. For the analysis, baseline Observation Carried Forward (BOCF) imputation will be used to impute data for visits after a patient has discontinued randomized treatment due to either of these reasons (even if data is present).
4. Population-level summary measure = Difference in least squares mean change from baseline in the weekly mean of the daily NRS score at Week 12, comparing each dose of NYX-2925 to placebo.

Any missing data at Week 12 that are not preceded by an intercurrent event (i.e., discontinuation of study drug due to AE or lack of efficacy) will remain as missing.

For the primary efficacy endpoint, the daily pain intensity NRS score from the handheld device will be averaged for baseline after randomization. Change from baseline will be assessed for

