6.11.3.2 Tipping Point Analysis

If the primary efficacy analysis in Section 6.11.2 significantly favors any NYX-2925 treatment group, a tipping point sensitivity analysis⁴ for the primary efficacy endpoint will be conducted to investigate how severe the departure from the MAR assumption data must be to overturn conclusion from the primary analysis.

In this analysis, the assumption will be that that missing data in the NYX-2925 groups follows a MNAR pattern. A tipping point-based approach will be used such that the trajectories of the subjects in the NYX-2925 groups after early withdrawal are assumed to be worse than placebo by a fixed amount (δ). The value of δ is the adjustment added during imputation to the change from baseline NRS scores at each visit after study discontinuation. This increment is added only to the imputed change from baseline NRS scores at visits after study discontinuation of the subjects in NYX-2925. The value of δ will increase in increments of 0.5 (i.e., 1.0, 1.5, 2.0) up to the point at which the treatment difference at Week 12 is no longer statistically significant. This analysis provides a measure of the degree by which the subjects in the NYX-2925 groups who discontinued early would need to be worse (compared to those who did not discontinue) at each post-discontinuation visit in order for the null hypothesis of no treatment difference to no longer be rejected. Intercurrent events will be imputed by BLOCF as estimand in Section 6.11.1.1. Each imputed dataset produced through PROC MI procedure will be processed as follows:

- All values imputed for the placebo group will remain unchanged
- All values imputed for the NYX-2925 groups will be incremented by a value of δ , which will vary from 0 up to a value by which statistical significance is not reached
- The modified data will be analyzed using similar analysis as described in Section 6.11.2.

Results will then be combined using PROC MIANALYZE and will consequently be recorded

The “tipping point” is defined as the value of δ at which the result changes from a statistically significant treatment effect to a treatment effect that is no longer statistically significant. The larger the value of δ , the more robust the conclusion from the primary analysis with respect to assumptions around missing data.

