2.5.2 New Text

Section 6.11.3.2 Tipping Point Analysis

If the primary efficacy analysis in Section 6.11.2 significantly favors any NYX-2925 treatment group, a tipping point sensitivity analysis⁴ for the primary efficacy endpoint will be conducted to investigate how severe the departure from the MAR assumption data must be to overturn conclusion from the primary analysis.

In this analysis, the assumption will be that that missing data and data occurring after an ICE in the NYX-2925 groups follows a MNAR pattern. A tipping point-based approach will be used such that the trajectories of the subjects in the NYX-2925 groups after early withdrawal

are assumed to be worse than placebo by a fixed amount (δ). The value of δ is the adjustment added during imputation to the change from baseline NRS scores at each visit after study discontinuation. This increment is added only to the imputed change from baseline NRS scores at visits after study discontinuation of the subjects in NYX-2925. The value of δ will increase in increments of 0.5 (i.e., 1.0, 1.5, 2.0) up to the point at which the treatment difference at Week 12 is no longer statistically significant. This analysis provides a measure of the degree by which the subjects in the NYX-2925 groups who discontinued early would need to be worse (compared to those who did not discontinue) at each post-discontinuation visit in order for the null hypothesis of no treatment difference to no longer be rejected. Each imputed dataset produced through PROC MI procedure will be processed as follow.

2.6 Change 6

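### The primary estimand is labelled treatment-policy but is a baseline-carried-forward composite, and no sensitivity or supportive analysis in force clearly keeps that rule

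*SAP*

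**What the plan says.** **Primary.** SAP Addendum 2.2.2, which replaces SAP 6.11.1.1, reads "The primary efficacy analysis will evaluate the treatment-policy estimand". It defines the intercurrent event (ICE) as stopping study drug for an adverse event (AE) or lack of efficacy before Week 12. It then applies baseline observation carried forward (BLOCF) to "visits after a patient has discontinued randomized treatment due to either of these reasons (even if data is present". Its opening sentence words the target as improvement "in subjects in the modified ITT population not discontinuing treatment early due to an AE or lack of efficacy through Week 12". Protocol 12.6.1 uses the same label but describes something else: "The treatment-policy estimand combines the improvement (reduction) from Baseline in the weekly mean of the daily NRS score and not discontinuing treatment early". Missing data not preceded by an ICE stay missing and are handled by the MMRM.

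**Other analyses in force.** Addendum 2.4.2 (pattern-mixture) imputes post-ICE data under MNAR. Addendum 2.5.2 (tipping point) assumes that "missing data and data occurring after an ICE in the NYX-2925 groups follows a MNAR pattern". Addenda 2.6.2, 2.7.2 and 2.8.2 say that the ANCOVA, the pooled-dose MMRM and the exploratory moderator models use no imputation.

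**What changed.** SAP V1.0, Section 6.11.3.2, said of the tipping point: "Intercurrent events will be imputed by BLOCF as estimand in Section 6.11.1.1". Addendum 2.5.1 reproduces that sentence as old text, and 2.5.2 omits it. Addendum Section 1 states that the changes came after database lock and unblinding. Its only relevant reason is to detail the BLOCF used in the primary analysis.

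**The concern.** A treatment-policy strategy would use the scores observed after discontinuation. This analysis overwrites them, so a reader who trusts the label will take the result as an effect regardless of stopping drug.

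The second problem is what the sensitivity analyses can show. SAP 6.11.3.1 presents the pattern-mixture model as a stress test of MAR in the primary analysis. Section 6.11.3.2 says that a larger delta means a conclusion more robust to missing-data assumptions. In the primary, however, post-ICE values are fixed at baseline and are not handled under MAR. Re-imputing them, or leaving them out, changes the intercurrent-event strategy as well as the missing-data assumption. Agreement or disagreement with the primary then cannot be put down to missing data alone. For the tipping point, this follows from a choice made with unblinded data available.

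**Working it through.** **1. Handling of AE and lack-of-efficacy discontinuations, in the plan in force**

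| Analysis of the primary endpoint | Source | Post-ICE visits |
|---|---|---|
| Primary MMRM | Addendum 2.2.2, 2.3.2 | BLOCF |
| Pattern-mixture | Addendum 2.4.2 | MNAR, control-based |
| Tipping point | Addendum 2.5.2 | MNAR; BLOCF sentence gone |
| ANCOVA | Addendum 2.6.2 | No imputation |
| Pooled-dose MMRM | Addendum 2.7.2 | No imputation |
| Moderator models | Addendum 2.8.2 | No imputation |

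Two analyses come near but do not fill the gap. The two-sided repeat of the primary (SAP 6.11.2) keeps BLOCF, but it is the same analysis at another test level. The cumulative-response analysis (SAP 6.11.4.8) gives 0% to all premature discontinuers, but it is a secondary endpoint with a broader rule.

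Clearly is the right qualifier for the tipping point. An unreplaced bullet in SAP 6.11.3.2 still points to Section 6.11.2, which now mentions BLOCF (Addendum 2.3.2). The timing of delta is also unsettled: Addendum 2.5.2 calls it an "adjustment added during imputation to the change from baseline NRS scores at each visit after study discontinuation", while the SAP bullet reads "All values imputed for the NYX-2925 groups will be incremented by a value of" delta, applied to data sets already imputed.

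**2. The plan's own figure.** SAP Section 4 gives 85 per arm, difference 0.73, SD 1.7 and one-sided 0.05. Power = Φ(0.73 / (1.7 × √(2/85)) − 1.645) = Φ(2.799 − 1.645) = 0.876, which reproduces the stated 88%. I take 0.73 and 1.7 from there.

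**3. Illustration of size.** The documents give no dropout rates, so these are assumptions:

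- Placebo Week 12 change −1.5, so drug −1.5 − 0.73 = −2.23.
- A further 10% of each arm drops out for other reasons.
- Dropouts are last observed at Weeks 3 to 8, with no diary data afterwards.
- Mean path over weeks proportional to 1 − exp(−week/3); covariance 1.7² × (0.6 + 0.4 × 0.85^lag).
- AE dropouts are random. Lack-of-efficacy dropouts are those with the worst last two observed weeks, plus N(0,1) noise.
- 400,000 simulated subjects per arm; site and baseline covariate left out.

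Primary: zero change after an ICE, other missing data by sequential regression with an arm term. Control-based: sequential regression fitted in placebo only. ANCOVA: observed Week 12 values.

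Hand check of the primary, for random AE dropout and no other missing data: difference = 2.23 × (1 − q_drug) − 1.5 × (1 − q_placebo).

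- 10% v 10%: 2.007 − 1.350 = 0.657
- 15% v 10%: 1.8955 − 1.350 = 0.546
- 10% v 15%: 2.007 − 1.275 = 0.732

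Simulated benefit at Week 12, with ranges running between all-AE and all-lack-of-efficacy dropout:

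| ICE rate, drug v placebo | Primary | Control-based | ANCOVA |
|---|---|---|---|
| 5% v 5% | 0.69 | 0.68 | 0.73 |
| 10% v 10% | 0.65 | 0.66 | 0.73 |
| 15% v 10% | 0.53-0.60 | 0.65 | 0.73-0.81 |
| 10% v 15% | 0.66-0.73 | 0.66 | 0.64-0.73 |

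The all-AE primary values (0.65, 0.53, 0.73 in the last three rows) agree with the hand check to within 0.02; the hand check leaves out the other dropouts. A separately coded repeat at 200,000 per arm matched the table to within about 0.01. Balanced rows come first because Protocol 6.3 reports no adverse-event difference from placebo in the earlier studies. The all-lack-of-efficacy end of 15% v 10% is a bound, not a likely case for an effective drug.

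**The case against.** The strongest reply is that the addendum moves the tipping point towards the protocol. Protocol 12.6.2 applies delta to NYX-2925 subjects after withdrawal, with no exception for BLOCF. V1.0's sentence was SAP-level detail, and it sat uneasily beside a delta applied at every visit after discontinuation. This stands: the new rule fits the protocol's wording.

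A reader might infer that the sentence was removed for no reason, or to favour the drug. The documents do not support that. Addendum Section 1 and Section 2.2.2 confine BLOCF to the primary analysis, and old and new text are shown side by side. What is missing is a separate justification for changing this analysis after unblinding.

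A reader might also infer that V1.0 left the pattern-mixture handling open. It did not: SAP 6.11.3.1 already sent NYX-2925 discontinuers to the placebo trajectory, whatever their reason for stopping. The addendum made the inclusion of post-ICE data explicit.

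Another tempting reading is that placebo discontinuers stay at baseline while drug discontinuers are modelled. It would have to apply the pointer to Section 6.11.2 to one arm only, although BLOCF there covers both. A neighbouring bullet in SAP 6.11.3.2 also expects imputed placebo values, left unchanged by delta. I put no size on that reading.

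Finally, the four estimand attributes are explicit, so the wrong label alters no estimate. The ANCOVA and pooled model are already filed as supportive in the SAP (Protocol 12.6.2 calls the ANCOVA a sensitivity analysis). Both points are fair and keep this below a mandatory change.

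**Conclusion.** The concern holds. The label contradicts the stated rule, and the target wording describes a subset although discontinuers stay in the analysis. The plan in force has no sensitivity or supportive analysis of the primary endpoint that clearly keeps the rule and varies only the other missing data. This should be corrected; it does not invalidate the primary analysis.

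Under the assumptions above, the primary and control-based results differ by only about 0.01 when dropout is balanced, which is no more than the simulation noise. With 15% v 10% dropout, the analysis that SAP 6.11.3.1 calls conservative is more favourable than the primary (0.65 against 0.53-0.60). With 10% v 15% it is equal or lower (0.66 against 0.66-0.73). A reader might infer that the sensitivity analyses consistently flatter the drug. The documents give no dropout rates and the direction turns on imbalance, so no consistent bias is claimed. The tipping point matters only if the primary is significant, because it is not run otherwise.

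**What to change.** 1. Rename the primary estimand composite: no change after AE or lack-of-efficacy discontinuation, other missing data under MAR. Delete the wording that limits the target to subjects not discontinuing.
2. If the tipping point runs, report the V1.0 version (BLOCF kept for those discontinuations, delta only on other missing data) beside the addendum version. Say that the addendum rule was set after unblinding and is also consistent with Protocol 12.6.2, and justify the change.
3. Because the tipping point is conditional on significance, add one pattern-mixture run that keeps BLOCF for those discontinuations and varies only the other missing data.
4. In SAP 6.11.3.1, limit the claim of conservatism to departures from MAR for missing data not preceded by an ICE. Describe the no-imputation ANCOVA and pooled MMRM as supplementary analyses under a different strategy.
5. State that placebo post-ICE data in the tipping point follow the same rule as the NYX-2925 groups, without delta, and whether delta is added during or after imputation.

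The cost is wording plus a few re-runs of existing programs on existing data. The added runs will themselves be post-unblinding and should be marked so. Supportive results may look less favourable.
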